4.9. Other Analyses

4.9.1. Subgroup analyses

The primary analysis of HES flare rate, key secondary endpoints and safety data will be summarised for all participants in the study and also summarised by age group (6 to 11 years and 12 to 17 years).

4.10. Interim Analyses

An analysis to present cumulative data may be completed if required, e.g. for early regulatory review.

4.11. Changes to Protocol Defined Analyses

Changes or deviations from the statistical analysis specified in the Protocol Amendment 4 (Dated: 16-Dec-2024) [[Document Number TMF-20082402](#)] are detailed in [Table 1](#).

Table 1 Changes to Protocol Defined Analysis Plan

Protocol Defined Analysis	SAP Defined Analysis	Rationale for Changes

As listed in the following protocol sections
 
 - Section 3 – Objectives and Endpoints - Section 8.1.3 – Reduction in Use of OCS, Immunosuppressive and/or Cytotoxic HES Therapy - Section 9.4.3 – Other Endpoints 
The protocol endpoint is defined as
 
 - Taking immunosuppressive and/or cytotoxic HES therapy at Week 52 in participants that are taking immunosuppressive and/or cytotoxic HES therapy at baseline 	
As listed in
 
 - Section 1.1 – Objectives and Endpoints - Section 4.4.3 - Taking immunosuppressive and/or cytotoxic HES therapy during Weeks 48 to 52 
The protocol endpoint is defined as
 
 - Taking immunosuppressive and/or cytotoxic HES therapy during Weeks 48 to 52 in participants that are taking immunosuppressive and/or cytotoxic HES therapy at baseline 	
For consistency in the reporting of other medication data (such as changes in OCS medication) during the final four weeks of the treatment period (Weeks 48 to 52) the changes in this endpoint will be summarized and tabulated during each four-week period from Weeks 0-4 through to Weeks 48-52.
 
The wording of this endpoint has therefore been clarified as 'during Weeks 48 to 52' rather than 'at Week 52' since this is considering all study days between Week 48 and Week 52 (as per Section 6.2.4.2) and this clarification has been added within each impacted sections of this analysis plan.

5. SAMPLE SIZE DETERMINATION

At least 15 participants aged 6 to 17 years will be enrolled. Due to the rare nature of HES in pediatrics, there is minimal data available to predict the age distribution in the study.

CCI

CCI

[figure not shown]
Sample size was chosen based on the expected precision of the estimate. No sample size reassessment is planned.

Expected Precision of Estimate

The expected variance in annualised flare rate has been estimated based on the data from the completed Study 205203, which used the same definition of HES flare. In that study, flare rate was estimated using the negative binomial model with the standard error (SE) expressed on the log scale, therefore the uncertainty around the expected point estimates of effect is presented in terms of 95% confidence intervals (CIs) rather than by the variance.

CCI

CCI The observed flare rate in Study 205203 was 0.26/year. If the same rate was observed in this study with 15 participants, the 95% CI would be (0.07, 0.93).

6. SUPPORTING DOCUMENTATION

6.1. Appendix 1: Study Population Analyses

Unless otherwise specified, the study population analyses will be based on the Full Analysis Set. A summary of the number of participants in each of the participant level analysis sets will be provided.

In this multi-centre global study, enrolment will be presented by region, country and site.

6.1.1. Participant Disposition

A summary of the screening status will be provided. Reasons for screen failure will be summarized. A summary of the number and percentage of participants who enrolled by country, site ID and investigator ID will be provided.

A summary of the number and percentage of participants who completed the study as well as those who prematurely withdrew from the study will be provided. Reasons for study withdrawal will be summarized.

A summary of study treatment status will be provided. This display will show the number and percentage of participants who have completed the scheduled study treatment, those who withdrew from treatment but continued follow-up, or have discontinued study treatment prematurely, as well as primary reasons for discontinuation of study treatment. The total number of scheduled treatments, on-treatment, off-treatment and missed treatment will be summarized in terms of subject years.

6.1.2. Demographic and Baseline Characteristics

The demographic characteristics including age, gender, height/weight, BMI at screening, race, race detail will be summarized. In addition, the following age categories will be summarized: 6-11 and 12-17 based on the Enrolled Analysis Set. Past medical conditions and current medical conditions as of screening will be summarized respectively.

A summary of baseline HES therapy, duration of HES, number of flares 12 months prior to screening, and baseline OCS doses will be summarized (refer section 6.2.1). The number of L-HES patients based on T-cell profile data and baseline laboratory information (including CD3-CD4+, Interleukin-5, Immunoglobulin E and blood eosinophil count data) will be summarized

If the summary of demographics meets the criteria for de-identification, as described in the relevant procedural document, a de-identification version will be produced.

6.1.3. Protocol Deviations

Important protocol deviations will be summarized.

Protocol deviations will be tracked by the study team throughout the conduct of the study. These protocol deviations will be reviewed to identify those considered as important as follows:

- Data will be reviewed prior to database lock to ensure all important deviations are captured and categorised in the protocol deviations dataset.
- This dataset will be the basis for summaries of important protocol deviations.

In addition to the overall summary of important protocol deviations, a separate summary of significant protocol deviations, categorized by those related and unrelated to the COVID-19 pandemic, will also be produced.

Visits and assessments missed due to the COVID-19 pandemic, together with visits conducted remotely, will be summarized.

6.1.4. Prior and Concomitant Medications

Concomitant medications will be coded using both the GSK Drug and WHO Drug dictionaries. However, the summary will be based on GSK Drug dictionary only. The summary of concomitant medications will be provided by ingredient, i.e. multi-ingredient medications will be summarized for each individual ingredient rather than a combination of ingredients. The summary will be created using ingredient base names, i.e. ingredients with the same base name but different salt will appear under one base name in the summary. Anatomical Therapeutic Chemical (ATC) classifications will not appear in the summary.

Concomitant medications include any medication that was taken at some point during the study.

6.2. Appendix 2: Data Derivations Rule

6.2.1. Oral Prednisone/Prednisolone or Equivalent Daily Dose

For each subject, oral prednisone equivalent daily dose (mg) on each day of the study will be identified from the concomitant medications form. Corticosteroids will be identified from the list of coded concomitant medications for the study, by merging with the GSK respiratory medication class (RMC) reference data set by component code. This reference data is created by dictionary specialists who identify a list of component terms for corticosteroids, which then undergo clinical review to ensure the correct classification is assigned.

Only corticosteroids recorded with route = “Oral” will be considered as oral corticosteroids. Subjects not receiving OCS therapy on any day of the study will be assigned a prednisone equivalent daily dose of 0 mg for that day. The corticosteroid conversion factors in the table below will be used to scale each corticosteroid dose to a prednisone equivalent dose.

Medication Name	Scaling Factor
Betamethasone	8.33
Budesonide ¹	0
Cortisone	0.2
Dexamethasone	6.67
Deflazacort	0.83
Hydrocortisone	0.25
Methylprednisone	1.25
Meprednisone	1.25
Prednisone	1
Prednisolone	1
Prednisone acetate	1
Triamcinolone	1.25

¹Budesonide has negligible systemic exposure and will be classed as “Other HES therapy” rather than oral corticosteroid therapy.

Where the frequency of the recorded corticosteroid dose is not once daily, the following calculations will be used to determine the daily dose.

Medication Frequency	Daily Dose Equivalent
BID	2 x dose
TID	3 x dose
QID	4 x dose
QOD	dose / 2
2XWK	(2 x dose) / 7
3XWK	(3 x dose) / 7
4XWK	(4 x dose) / 7
5XWK	(5 x dose) / 7

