 - IV or SC corticosteroids in the 4-week period prior to enrolment (Visit 2).
 - Any other monoclonal antibodies within 30 days or 5 half-lives, whichever is longer, of enrolment (Visit 2).

Other investigational product/clinical study

13. Participants who have received treatment with an investigational agent (biologic or non-biologic) within the past 30 days or 5 drug half-lives, whichever is longer, prior to enrolment (Visit 2). The term "investigational" applies to any drug not approved for sale in the country in which it is being used or investigational formulations of marketed products
14. Use of candidate COVID-19 vaccines that have not received limited, accelerated, or full authorisation/approval, and are only in use as part of a clinical trial
15. Participants who are currently participating in any other interventional clinical study

Contraindications

16. Participants with any history of hypersensitivity to any monoclonal antibody (including mepolizumab).

Other Exclusions

17. 12-lead ECG finding:

For all participants:

- An abnormal ECG finding from the 12-lead ECG conducted at Visit 1 if considered to be clinically significant and would impact the participant's participation during the study based on the evaluation of the investigator.

For participants aged 6 to 11 years:

- QT interval corrected using Fridericia's formula (QTcF) > 450 msec.
- Left bundle branch block.

For participant aged 12 to 17 years:

- QTcF > 450 msec or QT interval corrected for heart rate (QTc) > 480 msec in participants with bundle branch block.

NOTE: 12-lead ECG results performed centrally or by the local 12-lead ECG machine at Screening (Visit 1) over-read by the centralised independent cardiologist must be received prior to assessing eligibility at Visit 2 by the investigator.

18. Liver abnormality/disease:

- Alanine aminotransferase (ALT) >2.5 × upper limit of normal (ULN) or ALT >5 × ULN if documented HES with liver manifestations
- Bilirubin >1.5 × ULN (isolated bilirubin >1.5 × ULN is acceptable if bilirubin is fractionated and direct bilirubin <35%)
- Current or chronic history of liver disease or known hepatic or biliary abnormalities (with the exception of Gilbert's syndrome or asymptomatic gallstones)
- Presence of hepatitis B surface antigen (HBsAg) at Screening or within 3 months prior to first dose of study intervention
- Positive hepatitis C antibody test result at Screening or within 3 months prior to first dose of study intervention

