8.1.1. HES Flare

A HES flare is defined as a HES-related clinical manifestation based on a physician documented change in clinical signs or symptoms (worsening symptoms and/or elevated blood eosinophil level) resulting in the need for either of the following:

- An increase from the most recent dose in the maintenance OCS dose (prednisone/prednisolone equivalent) by at least 10 mg/day for 5 days
- An increase in or addition of any immunosuppressive and/or cytotoxic HES therapy from/to the most recent dose of HES therapy.

To be considered as a HES flare, the most recent dose of HES therapy must not have changed for at least 4 weeks prior to the flare. This ensures that failed reductions in HES therapy are not misclassified as a HES flare.

The start date for a HES flare will be defined as the date of therapy escalation confirmed by the investigator attributable to a HES-related clinical manifestation.

When a participant experiences a HES flare, the investigator will monitor the change in disease control per routine medical care (e.g., follow-up call) and record the resolution of the flare including the end date. Investigators are encouraged, as medically appropriate, to return the participant's treatment regimen to the level prior to the flare after the flare has resolved.

In the event of disease worsening for which the investigator suspects a HES flare between scheduled clinic visits, when possible, the participant will return to the clinic to have the unscheduled 'Flare' visit assessment completed as described in the SoA. When attending the clinic visit at the time of a suspected HES flare is not possible, the investigator should make every effort to evaluate the participant via telephone and complete the CCI [REDACTED]. If an escalation of therapy is initiated by a non-study physician, the investigator should confirm that the escalation in therapy is attributable to a HES-related clinical manifestation.

CCI

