An additional estimand for this endpoint will use the whole population of participants with HES aged 6 to 17 years.

4.3.2. Reduction of $\geq 50\%$ in mean daily OCS dose (prednisone/prednisolone or equivalent) from Weeks 0 to 4 compared with Weeks 48 to 52

Derivation of Endpoint

Participants who achieve a mean daily OCS dose (prednisone/prednisolone or equivalent) reduction of 50% or more from Week 0-4 to each 4-week period from Weeks 4-8 through to Weeks 48-52 will be determined based on the change in mean OCS dose defined in Section 4.3.1. For each 4-week period a reduction of 50% or more is defined as:

$$\frac{\text{Mean OCS dose} - \text{Mean OCS dose during Week 0 to 4}}{\text{Mean OCS dose during Week 0 to 4}} \times 100 \leq -50$$

The estimand for this endpoint is described in Section 1.1 and summarised below.

Target Participant Population	Participants with HES aged 6 to 17 years that are taking OCS at baseline, i.e. mean Week 0 to 4 OCS dose >0 mg/day.
Endpoint	Reduction of ≥50% in mean daily OCS dose (prednisone/prednisolone or equivalent) from Weeks 0 to 4 compared with Weeks 48 to 52.
Intercurrent events	The anticipated intercurrent events and corresponding strategies are:- 
 • Study treatment discontinuation: treatment policy strategy. • Changes to OCS therapy: composite strategy (part of endpoint). • Other changes to background HES medication which might modulate the disease course of HES, determined either by published data or by proposed or known mechanism of action: treatment policy strategy.
Summary measure	Proportion of participants with reduction of ≥50% in mean daily OCS dose (prednisone/prednisolone or equivalent) from Weeks 0 to 4 compared with Weeks 48 to 52.

Main Analytical Approach

The number and percentage of participants who achieve a reduction in mean daily OCS (prednisone/prednisolone or equivalent) dose of 50% or more during Week 48 to 52 will be presented by treatment group. The number and percentage of participants who achieve a reduction in mean daily OCS dose of 50% or more during each 4-week period from Weeks 0-4 to each 4-week period from weeks 4-8 through to Weeks 48-52 will also be tabulated.

Participants withdrawing prematurely from the study who have no available data during Weeks 48 to 52 will be summarised as not having met the endpoint criteria, i.e., a treatment failure. The same approach will be used for the summary for each of the other 4-week periods.

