6.2.1.1. Mean Daily OCS Dose

The change in the mean daily OCS dose from Weeks 0-4 to Weeks 48-52 will be calculated as follows:

The mean daily OCS dose for weeks 0-4 will be calculated as:

$$\frac{\text{Sum of daily OCS dose for weeks 0 – 4}}{28}$$

The mean daily OCS dose for weeks 48-52 will be calculated as:

$$\frac{\text{Sum of daily OCS dose for weeks 48 – 52}}{28}$$

The change in the mean daily OCS dose from Weeks 0-4 to Weeks 48-52 will be the difference of mean daily OCS dose for weeks 48-52 minus mean daily OCS dose for Weeks 0-4.

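### Parenteral corticosteroid that replaces oral dosing in Weeks 48-52 lowers the mean daily OCS dose and can create an OCS responder with no real steroid reduction

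*SAP*

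**What the plan says.** SAP 6.2.1 builds the daily dose from concomitant medication records. On route it states: "Only corticosteroids recorded with route = “Oral” will be considered as oral corticosteroids". On days without such a record it states: "Subjects not receiving OCS therapy on any day of the study will be assigned a prednisone equivalent daily dose of 0 mg". SAP 6.2.1.1 sums the daily doses in each window and divides by 28. SAP 6.2.4.2 sets the windows: Weeks 0-4 run from the day after first dose to 28 days after it, and Weeks 48-52 from 337 to 364 days after it.

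The window means feed the change in dose (SAP 4.3.1), the 50% reduction responder (4.3.2) and the 7.5 mg responder (4.3.3). The only rule in 4.3.2 and 4.3.3 that makes a participant a failure regardless of dose is premature withdrawal with no data in the window. Changes in OCS are part of the endpoint; other changes in background HES medication follow treatment policy.

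Protocol 6.8 lets investigators adjust standard of care from Visit 3 and does not list parenteral corticosteroid among the therapies barred on study. Exclusion criterion 12 restricts IV and SC corticosteroid only in the 4 weeks before Visit 2.

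The corticosteroid limb of the flare definition (Protocol 8.1.1, SAP 4.2.1) reads: "An increase from the most recent dose in the maintenance OCS dose (prednisone/prednisolone equivalent) by at least 10 mg/day for 5 days". The other limb covers starting or increasing immunosuppressive or cytotoxic HES therapy. Neither mentions parenteral corticosteroid.

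**The concern.** The OCS endpoints will be read as evidence of steroid sparing. A participant whose oral corticosteroid is replaced by parenteral corticosteroid for part of Weeks 48-52, possibly because the disease is worsening, scores zero on those days. Nothing in the visible derivation offsets this: the parenteral dose is not converted, and its use is not a failure. Following the rule exactly can therefore score a participant with undiminished systemic exposure as a success.

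The same applies to the whole-population version of the 7.5 mg endpoint. A participant on no oral corticosteroid but receiving parenteral corticosteroid in the window scores 0 mg and counts as a responder.

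The standard displays need not reveal it. SAP 6.1.4 summarises concomitant medication by ingredient base name and specifies no split by route.

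**Working it through.** The plan states no figure on this point, so there is nothing to reproduce. The check applies the SAP's own rule to assumed doses, because the documents give none.

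**Inputs.** Oral route only, and 0 mg on a day without oral corticosteroid (SAP 6.2.1). Divisor 28 (SAP 6.2.1.1). Responder if the change is -50% or lower (SAP 4.3.2), or if the mean is 7.5 mg or less (SAP 4.3.3). At least 15 participants (SAP 5).

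**Replacement.** Let B be the oral dose in mg/day throughout Weeks 0-4. In Weeks 48-52 it is replaced on d of 28 days by parenteral corticosteroid of equal prednisone-equivalent dose.

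- SAP mean = B × (28 − d)/28
- SAP change = −d/28
- All-route mean = B, so the true change is 0%

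| B (mg/day) | d | SAP mean | SAP change | 50% responder | 7.5 mg responder | All-route mean |
|---|---|---|---|---|---|---|
| 10 | 7 | 7.5 | −25% | no | yes | 10 |
| 10 | 14 | 5.0 | −50% | yes | yes | 10 |
| 15 | 14 | 7.5 | −50% | yes | yes | 15 |
| 20 | 14 | 10.0 | −50% | yes | no | 20 |
| 20 | 18 | 7.1 | −64% | yes | yes | 20 |
| 40 | 23 | 7.1 | −82% | yes | yes | 40 |

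Fourteen parenteral days meet the 50% criterion whatever B is. In the 15 mg case the participant also contributes −7.5 mg/day to the mean change instead of 0.

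**Mixed days.** The oral dose still counts; only the parenteral part is ignored. With 5 mg/day oral and a parenteral total of P mg over the window, the SAP mean is 5 mg whatever P is. The all-route mean is 5 + P/28, which exceeds 7.5 mg once P exceeds 2.5 × 28 = 70 mg.

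**A case where the zeros do not decide everything.** Take 20 mg/day at baseline, then 18 days on 10 mg oral and 10 parenteral-only days. The SAP mean is 180/28 = 6.4 mg, a success on both endpoints. Ten mg on all 28 days would already be a 50% fall, so that success is false only if the parenteral total exceeds 280 − 180 = 100 mg. The 7.5 mg success is false once the total exceeds 210 − 180 = 30 mg.

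**Opposite direction.** Parenteral replacement in Weeks 0-4 lowers the baseline. With 15 mg/day replaced on 14 days, baseline scores 7.5 mg. A later true fall to 7.5 mg/day oral then scores as no change. A baseline mean of 0 removes the participant from the OCS subpopulation altogether.

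**Weight of one participant.** 1/15 = 6.7 percentage points in the whole population. The number taking OCS at baseline is not given; if it were 8 (assumption), 1/8 = 12.5 points.

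**The case against.** The strongest reply is that the endpoints are named as oral corticosteroid endpoints and the estimand is pre-specified: OCS changes enter the endpoint, and other background changes follow treatment policy. Parenteral corticosteroid can be read as falling under the latter. That stands, and it is why the named endpoints should not be replaced. It does not answer how the result will be read. The SAP itself drops oral budesonide because its systemic exposure is negligible, so systemic exposure already guides what counts; parenteral systemic corticosteroid has that exposure and still scores nothing.

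Two further points stand. No frequency of on-study parenteral use is given, so it may be rare. SAP 4.4, part of 4.1.2 and the protocol section after 9.4.2 are redacted, so supportive handling there cannot be excluded. The visible rules for the secondary endpoints contain none.

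A reader might infer three stronger things that the documents do not support:

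- *That the bias must favour mepolizumab because the baseline window is protected by exclusion 12.* That criterion covers the 4 weeks before Visit 2, while Weeks 0-4 start the day after first dose. Only the rule that standard of care is adjusted from Week 4 limits that window, and error there runs the other way.
- *That every day on parenteral corticosteroid scores 0 mg.* Only days with no oral corticosteroid do.
- *That parenterally treated worsenings drop out of the primary flare count.* Flares come from the investigator's flare form, not from the SAP 6.2.1 derivation. The text does not say whether the immunosuppressive limb covers parenteral corticosteroid, and a later qualifying oral increase would still meet the OCS limb. The definition is also kept the same as in Study 205203 for comparison (Protocol 4.2). This is an ambiguity, not a demonstrated loss of flares.

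**Conclusion.** The concern holds for the OCS endpoints. Under SAP 6.2.1, parenteral corticosteroid that replaces oral dosing in Weeks 48-52 lowers the score and can turn a participant with no real reduction into a responder on both criteria. The 15 mg, 14-day case shows this with nothing assumed beyond the dose, equal-dose substitution, and an oral record that stops on the parenteral days.

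The size per case is 6.7 points (15 participants) to 12.5 points (8, assumed). The total size and its net direction cannot be stated, because parenteral use is unknown and use in Weeks 0-4 works the other way. For flares, the finding is only that the definition is silent on parenteral corticosteroid. This is a cheap improvement, not a flaw that invalidates the named endpoints.

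**What to change.** Leave the oral endpoints and the flare definition unchanged. Before database lock:

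1. Add to SAP 6.2.1 an all-route systemic corticosteroid daily dose (oral plus IV, IM and SC, in prednisone equivalents), and repeat the summaries in 4.3.1 to 4.3.3 with it as a supportive analysis.
2. First extend the tables it needs. The conversion table lists methylprednisone but has no methylprednisolone row, and the frequency table has no rule for a single or depot injection. State the factor and the days assigned for each.
3. In SAP 4.2, state which limb of the flare definition, if any, covers parenteral corticosteroid, and report the number of HES worsenings treated parenterally that were not counted as flares.

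The data should already exist: Protocol 6.8 requires reason, dates, dose and frequency for each medication, and SAP 6.2.1 relies on a recorded route. The cost is SAP wording, one extra derivation and one extra set of tables.
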